4.2.10 Safety outcome variables

All safety variables will be summarised using the safety analysis set and data presented according to actual treatment received.

4.2.10.1 Adverse events (AEs)

AEs will be summarised separately for the on-study, on-treatment, and post-treatment periods, as defined in Section 3.6.1. All AEs will be listed for each patient, regardless of treatment period. All summaries will be presented by treatment group.

An overall summary table will be produced showing the number and percentage of patients with at least one AE in each of the following categories: AEs, serious adverse events (SAEs), AEs with outcome of death, and AEs leading to discontinuation of IP (DAEs). This summary will also be repeated by baseline blood eosinophil count ($<300/\mu\text{L}$, $\geq 300/\mu\text{L}$) for the on-study and on-treatment periods. The total number of AEs in the different AE categories in terms of AE counts will also be presented (i.e., accounting for multiple occurrences of the same event in a patient).

AEs, AEs with outcome of death, SAEs and DAEs will be summarised by SOC and PT assigned to the event by MedDRA. For each PT, the number and percentage of patients reporting at least one occurrence will be presented, i.e., for a patient multiple AE occurrences of the same PT will only be counted once. Presentations for AEs and SAEs by SOC and PT will also be repeated for baseline blood eosinophil count ($<300/\mu\text{L}$, $\geq 300/\mu\text{L}$) for the on-study and on-treatment periods.

The rate of AEs per patient-years at risk, calculated as (number of patients reporting AE)/(total period with patients at risk of AE), will also be reported by treatment group for the on-study and on-treatment periods. The total period with patients at risk of AE for the on-study and on-treatment periods will be defined as the sum of the on-study and on-treatment period across all patients in the treatment group, respectively. Rates will be expressed in terms of events per 100 patient-years.

A summary of the most common (frequency of $\geq 3\%$ in any treatment group) AEs will be presented by PT. AEs will be summarised by PT and maximum intensity. If a patient reports multiple AE occurrences of the same PT within the same study period, the maximum intensity will be taken as the highest recorded maximum intensity (the order being mild, moderate, and severe). AEs, SAEs and DAEs causally related to IP as assessed by the Investigator will be summarised by PT. The summary of related AEs and related SAEs will also be repeated for baseline blood eosinophil count ($<300/\mu\text{L}$, $\geq 300/\mu\text{L}$) for the on-study and on-treatment periods.

AEs of injection site reactions (high level term of injection site reaction) and hypersensitivity (standardised MedDRA query of hypersensitivity based on the latest MedDRA version) will be summarised by PT. The summary of AEs of hypersensitivity will be repeated for baseline blood eosinophil count ($<300/\mu\text{L}$, $\geq 300/\mu\text{L}$) for the on-study and on-treatment periods. The

hypersensitivity AEs causally related to IP as assessed by the Investigator will also be summarised by PT.

Separate listings of patients with AEs, AEs with outcome of death, SAEs, or DAEs will be presented.

Adjudicated events (major adverse cardiac events [MACE] and malignancies) will be summarised by treatment group and listed.

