1.2 Study design

This is a randomised, double-blind, parallel group, placebo-controlled study designed to evaluate the efficacy and safety of a fixed 30 mg dose of benralizumab administered subcutaneously for patients with a history of asthma exacerbations and uncontrolled asthma receiving medium to high-dose ICS/LABA with or without OCS and additional asthma controllers.

Approximately 666 patients will be randomised, of which at least 70% patients will be from China (including the mainland of China and Taiwan). The randomisation will be stratified by country/region (the mainland of China, Taiwan, South Korea or Philippine), age group (adult or adolescent), and peripheral blood eosinophil count at time of Visit 1 (<300 or \geq 300 cells/ μ L).

All the patients will be randomised to either placebo or benralizumab in a 1:1 ratio, every 4 weeks for the first 3 doses and then every 8 weeks thereafter. Study recruitment will be closed when recruitment is closed for all strata, based on the following strata closure process:

1. The eosinophil <300/ μ L stratum will be closed to the patients from China when the total number of Chinese patients in the eosinophil <300/ μ L stratum reaches approximately 166.
2. The eosinophil <300/ μ L stratum will be closed to the patients from all countries when the total number of patients in the eosinophil <300/ μ L stratum reaches approximately 222.
3. The whole study will be closed for recruitment when the total number of patients in the eosinophil \geq 300/ μ L stratum reaches approximately 444, with at least 70% Chinese patients in the stratum.

After initial enrolment and confirmation of entry criteria, patients will proceed to the run-in period of a minimum 4 weeks to allow adequate time for all of the eligibility criteria to be evaluated. Patients who meet eligibility criteria will be randomised to a 48-week treatment period. Patients will be maintained on their currently prescribed medium to high-dose ICS/LABA therapy and other asthma controllers, without change, from visit 1 until the end of the study.

A follow-up visit will be conducted at Week 56.

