3.6.1 Adverse events (AEs)

AEs experienced by the patients will be collected throughout the entire study and will be coded using the latest version of the Medical Dictionary for Regulatory Activities (MedDRA) per the Data Management Plan.

For analysis, AEs will be categorised according to their onset date into the following study periods:

- AEs in the on-study period are defined as those with onset date between the date of first dose of study treatment and the date of study completion or withdrawal from study, inclusive.
- AEs in the on-treatment period are defined as those with onset date between the date of first dose of study treatment and the date of scheduled EOT visit or IPD visit (for those patients who prematurely discontinue study treatment), inclusive. In the event that the EOT or IPD visit is completed beyond the protocol-defined visit window, AE with onset date after the date of last dose of study treatment + 8 weeks + 7 days will be excluded from the on-treatment period and instead assigned to the post-treatment period.
- AEs in the post-treatment period are defined as those with onset date in the on-study period but after the on-treatment period defined above.

For instances where a patient attends the follow-up visit without an earlier IPD visit or EOT visit, AEs occurring on or before the date of last dose of study treatment +8 weeks will be assigned to the on-treatment period, while AEs with onset date after this time will be assigned to the post-treatment period.

If an AE has a completely missing onset date then unless the stop date of the AE indicates otherwise, this AE will be considered an on-treatment event. Similarly, if an AE has a partial onset date, then unless the partial onset date or the stop date indicates otherwise, this will be considered an on-treatment AE.

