Two additional sensitivity analyses of the primary endpoint will be carried out to compare annual asthma exacerbation rates in the benralizumab group with those in the placebo group during the pre-pandemic phase and the during-pandemic phase respectively. The first analysis will use the pre-pandemic data only, i.e., all observed data over the 48-week treatment period (see Section 3.2) up to and including the day prior to the start date of pandemic. The second analysis will use the during-pandemic data only, i.e., all observed data from the start date of pandemic until the end of 48-week treatment period. These analyses will use all observed data in the specific COVID-19 phase regardless of adherence to randomised treatment or the use of an alternative treatment.

All these sensitivity analyses will use the similar negative binomial model as specified for the primary analysis (see Section 4.2.5.1). The response variable will be the number of exacerbations experienced by a patient during the follow-up for exacerbation in the specific COVID-19 phase. The logarithm of the patient’s corresponding follow-up time in the specific COVID-19 phase will be used as an offset variable in the model. The model will include

covariates of treatment group, region (China/Non-China), number of exacerbations in the year before the study, and the use of maintenance oral corticosteroids (yes/no).

Asthma exacerbation summary statistics as described in Section 4.2.5.2 will also be repeated by pandemic phase: pre-pandemic, during-pandemic.

AEs

All AE-related analyses described below will be based on the safety analysis set using the on-treatment period (see Section 3.6.1).

The overall AE summary table (AEs in any category reported) will be repeated by pandemic phase: pre-pandemic, during-pandemic. Categories will include: any AEs, SAEs, AEs with outcome of death, DAEs, COVID-19 AEs (as defined by standardised MedDRA query of COVID-19 based on the latest MedDRA version) and non-COVID-19 AEs.

Summaries of AEs and SAEs by SOC and PT along with the rates per patient-years at risk will be provided by pandemic phase: pre-pandemic, during-pandemic. Summaries of COVID-19 AEs and non-COVID-19 AEs by SOC and PT along with the rates per patient-years at risk will be provided for the during-pandemic phase.

If there are more than 10 patients reporting COVID-19 AEs, then the AE listing will be repeated including only these patients, with details of all AEs reported by these patients.

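### The AE rate counts patients over everyone's full period but is labelled as events and as time at risk; label and formula contradict each other, and phase-specific rates are not comparable for common AEs

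*SAP*

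**What the plan says.** Section 4.2.10.1 introduces "The rate of AEs per patient-years at risk" and fixes three things about it.

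- **Formula:** the rate is "calculated as (number of patients reporting AE)/(total period with patients at risk of AE"), so each patient counts at most once.
- **Denominator:** the total period is "defined as the sum of the on-study and on-treatment period across all patients in the treatment group, respectively". Nothing ends a patient's time at the first AE.
- **Unit:** "Rates will be expressed in terms of events per 100 patient-years".

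Section 3.6.1 defines on-study AEs as "those with onset date between the date of first dose of study treatment and the date of study completion or withdrawal from study, inclusive". Section 1.2 puts the follow-up visit at Week 56, after a 48-week treatment period.

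The overall summary in Section 4.2.10.1 also gives numbers and percentages of patients and adds: "The total number of AEs in the different AE categories in terms of AE counts will also be presented". Those counts are not divided by patient-years.

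Appendix 8.4 uses the same kind of rate again: "Summaries of AEs and SAEs by SOC and PT along with the rates per patient-years at risk will be provided by pandemic phase". It gives no other formula.

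**The concern.** Two coherent rates are available. An event rate divides all events by all follow-up time. A first-event incidence rate divides patients with the event by the time until each patient's first event, or the end of the period if there is none. Section 4.2.10.1 takes its numerator from the second and its denominator from the first, and gives the result the unit of the first and the at-risk wording of the second. A programmer who follows the text exactly will print a safety table whose unit does not describe its content.

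The SAP handles this coherently elsewhere. The crude exacerbation rate in Section 3.2 divides the number of exacerbations by total follow-up. The time-at-risk analysis in Section 4.2.5.2 removes days on which a new exacerbation cannot be counted. The AE rate does neither.

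Two things are at stake. A reader who takes the label at face value will read common AEs as less frequent per patient-year than they are. And a person-time rate is meant to make periods of different length comparable, which this one does not do. That affects the on-study against on-treatment rates and, above all, the pre-pandemic against during-pandemic rates.

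**Working it through.** The SAP states no AE rate and no expected AE frequency, so there is no figure to reproduce. The shares of patients affected, the hazards and the phase lengths below are assumptions.

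**Inputs.** On-study period for a completer: 56 weeks, T = 56 × 7 / 365.25 = 1.073 years. Treatment period: 48 weeks, T = 48 × 7 / 365.25 = 0.920 years. p = share of patients with the AE.

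**Direction, from the definitions alone.** The first-event incidence rate has the same numerator over a denominator that is no larger. The event rate has the same denominator under a numerator that is no smaller. So the SAP value cannot exceed either. With full follow-up it is also capped at 100/T: 93.2 per 100 patient-years over 56 weeks and 108.7 over 48 weeks, however many AEs occur.

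**Size, constant hazard.**

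- SAP value = 100 × p / T
- Incidence rate = 100 × (−ln(1 − p)) / T
- Shortfall = 1 − p / (−ln(1 − p)), which does not depend on T

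Worked case, p = 50%, 56 weeks: 50 / 1.073 = 46.6; 69.3 / 1.073 = 64.6; shortfall 1 − 0.5 / 0.693 = 28%.

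| Patients affected | SAP value | Incidence rate | Shortfall |
|---|---|---|---|
| 1% | 0.9 | 0.9 | 0.5% |
| 3% | 2.8 | 2.8 | 1.5% |
| 10% | 9.3 | 9.8 | 5% |
| 30% | 28.0 | 33.2 | 16% |
| 50% | 46.6 | 64.6 | 28% |
| 70% | 65.2 | 112.2 | 42% |
| 80% | 74.5 | 150.0 | 50% |

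Under a Poisson process the event rate equals the incidence rate. When events cluster within patients, it is higher. A simulation with gamma frailty (shape 1) at p = 70% gave 65 by the SAP formula, 126 as an incidence rate and 217 as an event rate.

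**Dependence on period length.** Hold the hazard at an assumed 1.5 per year, identical throughout. The SAP value is 100 × (1 − exp(−1.5 T)) / T:

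| Period | SAP value per 100 patient-years |
|---|---|
| 0.25 years in a phase | 125 |
| 0.75 years in a phase | 90 |
| 48 weeks | 81 |
| 56 weeks | 75 |

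The incidence rate is 150 in every row. The differences come only from the length of the period.

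**Between-arm ratio.** For an assumed 70% against 80%, the SAP formula gives 0.70 / 0.80 = 0.875, and the incidence-rate ratio is ln(0.30) / ln(0.20) = 0.748. For 12% against 10% the two are 1.20 and 1.21.

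**The case against.** The formula is explicit. The amendment history records that Edition 3 clarified the total period, so the at-risk period is a defined term and a programmer can produce exactly one number. Patients per unit of total follow-up is an intelligible crude measure, and preferring time to first event is a choice of measure. This stands as a defence of the quantity. It does not defend the unit, because no definition turns a patient count into events, and it does not remove the dependence on period length.

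A reader might infer that a real safety imbalance would be hidden because the between-arm ratio moves towards 1. The document does not support that. With similar follow-up in both arms, the ratio is essentially the risk ratio already visible in the percentages reported in the same section. A risk ratio nearer 1 than a rate ratio is a different measure and does not conceal anything. Total AE counts by category are shown as well.

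The larger shortfalls arise only at high frequencies, which suit the any-AE row but few individual PTs. At the 3% cut-off that the SAP uses for its most common AEs, the effect is negligible. Safety is summarised descriptively and the testing hierarchy in Section 4.1.1 contains no safety hypothesis.

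Finally, stopping time at the first AE makes the denominator depend on onset dates. Appendix 8.2 sets some partial onset dates to the day of first treatment, and Section 3.6.1 counts AEs with wholly missing onset dates as on-treatment by default. This is a fair warning about one of the remedies, and the fix has to deal with it.

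**Conclusion.** The point holds as a contradiction between formula and label, with one consequence beyond wording. The contradiction and the direction (never above either standard rate) follow from the text and need no assumption. The size does rest on assumptions: under a constant hazard the shortfall is trivial for uncommon AEs and substantial only when roughly a third or more of patients are affected. For those common AEs, the rates by pandemic phase, and on-study against on-treatment, can differ with no difference in risk. How far they would differ depends on the phase lengths and hazards, which the SAP does not give.

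Severity is minor to moderate. It would go too far to say that the safety conclusions are compromised: no test uses the rate, and the percentages and counts stand.

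**What to change.** Choose one definition in Section 4.2.10.1 and use it throughout.

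- **(a)** Number of AEs divided by total period, keeping the unit *events per 100 patient-years* and dropping *at risk*. This needs only AE counts for each row of the table.
- **(b)** Patients with the AE divided by the summed time from period start to the first such AE, or to the end of the period if there is none, labelled *patients with event per 100 patient-years at risk*. This needs a stated rule for missing and imputed onset dates.
- **Minimum, if the formula is kept:** relabel it *patients with an AE per 100 patient-years of total follow-up*, and drop both *events* and *at risk*.

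State in Appendix 8.4 that the same definition applies. If phases are to be compared there, use (a) or (b), because relabelling alone leaves the dependence on phase length.

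No new data are needed. Relabelling costs a sentence, and (a) costs little more. The cost of (b) is added programming, since time to first event has to be derived for every SOC and PT, by period and by phase.

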4.2.10.2 Laboratory data

All continuous laboratory parameters will be summarised descriptively by absolute value at each visit by treatment group, together with the corresponding change from baseline. All parameters will be summarised in SI units. Blood eosinophil counts, AST, ALT, ALP and GGT will be summarised in both SI and conventional units. Results which are reported from the central laboratory in conventional units will be converted to SI units for reporting.

Central laboratory reference ranges will be used for the identification of abnormalities, and a shift table will be produced for each laboratory parameter to display low, normal, high, and missing values. The shift tables will present baseline and maximum/minimum post-baseline value, as applicable for each parameter and will include patients with both baseline and post-baseline data.

Shift plots showing each individual patient's laboratory value at baseline and at maximum/minimum post-baseline will be produced for each continuous laboratory variable. If any laboratory variables show any unusual features (high or low values or a general shift in the data points) at other time points, then shift plots of these data may be produced.

Data for patients who have post-baseline values outside central laboratory reference ranges will be presented. This data presentation will include all visits for this subset of patients.

Maximum post-baseline total bilirubin elevations by maximum post-baseline ALT and AST will be presented. Total bilirubin will be presented in multiples of ULN (≤ 1.5 , $>1.5-2$, $>2 \times$ ULN), and ALT and AST will be presented in multiples of ULN (≤ 1 , $>1-3$, $>3-5$, $>5-10$, $>10 \times$ ULN).

Maximum post-baseline total bilirubin will be presented (<2 and $\geq 2 \times$ ULN) and plotted against maximum post-baseline ALT (<3 , $\geq 3 - <5$, $\geq 5 - <10$, and $\geq 10 \times$ ULN), expressed as multiples of ULN. This will be repeated to show maximum post-baseline total bilirubin against maximum post-baseline AST.

Data for patients with ALT or AST $\geq 3 \times$ ULN, and total bilirubin $\geq 2 \times$ ULN will be presented, which will include all visits for this subset of patients. A line plot of liver biochemistry test results (including ALP, ALT, AST, total bilirubin, and GGT) over time will also be presented for this subset of patients.

For all patients who meet the biochemical criteria for confirmed Hy's law (see CSP Appendix C), a Patient Safety Narrative will be produced, and the relevant laboratory parameters will be tabulated showing all visits for these patients.

A summary of shifts from baseline to maximum post-baseline CTCAE grade will be produced using CTCAE version 4.03 (June 14, 2010) or above for White blood cell counts and its components. The summary of shifts from baseline to maximum grade post-baseline will be produced, with results categorised as no grade, grades 1 to 4. White blood cells tests included in these summaries are: neutrophils, lymphocytes, and leukocytes. These will be from the complete blood count reports and will be done by absolute count.

For urinalysis data, a shift table will be generated to present changes from baseline to maximum post-baseline value for each parameter and will include patients with both baseline and post-baseline data.

Any data outside the central laboratory normal reference ranges will be explicitly noted on the listings that are produced.

4.2.10.3 Vital signs

Descriptive statistics for the absolute value at each visit and corresponding change from baseline for vital signs data will be presented for each treatment group. Baseline to maximum post-baseline and baseline to minimum post-baseline value shift tables will be generated, as applicable for each parameter and will include patients with both baseline and post-baseline data.

All recorded vital signs data will be listed.

4.2.10.4 Local electrocardiograms (ECGs)

The Investigator's assessment of the 12-lead ECG (normal, borderline or abnormal) will be listed for all patients, detailing whether any abnormalities were clinically significant or not.

A shift table will be produced to display normal, abnormal – not clinically significant, abnormal – clinically significant and not done. For this purpose, borderline will be grouped with normal. The shift table will present baseline and last observation post-baseline.

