Derivation of primary or secondary endpoints	31/Jan/2023	Section 3.1.1: Clarified the derivation of “last 14 days” in the baseline for daily assessments.	N/A	Provided additional clarification. No change to analysis.
Derivation of primary or secondary endpoints	31/Jan/2023	Section 3.1.1: Removed the text regarding the baseline definition for ACQ-6, SGRQ and safety laboratory.	N/A	Removed redundant text for simplification. The general definition of baseline applies to ACQ-6, SGRQ and safety laboratory.
Derivation of primary or secondary endpoints	31/Jan/2023	Section 3.1.1: Added text to clarify that safety data collected on the day of first IP dosing without assessment time will be treated as pre-dose in baseline derivation.	N/A	Provided additional clarification. No change to analysis.
Derivation of primary or secondary endpoints	31/Jan/2023	Section 3.1.1: Removed text regarding the baseline derivation for categorical (yes/no) respiratory disease characteristics.	N/A	Removed as not applicable. Respiratory disease characteristics are

Category*: Change refers to	Date	Description of change	In line with the CSP?	Rationale
				only collated at enrolment.
Derivation of primary or secondary endpoints	31/Jan/2023	Section 3.1.1: Updated that the blood eosinophil count used for randomisation stratification will be used for baseline in analysis, except for the analyses of change from baseline and percent change from baseline.	N/A	Provided clarification for the definition of baseline blood eosinophil counts for various analyses.
Derivation of primary or secondary endpoints	31/Jan/2023	Section 3.1.2: Addition of Section 3.1.2 for the definition of change from baseline.	N/A	Provided additional clarification. No change to analysis.
Derivation of primary or secondary endpoints	31/Jan/2023	Section 3.1.3: Removed local ECG from visit window definitions.	N/A	Removed as not applicable. No by-visit summary for local ECG.
Derivation of primary or secondary endpoints	31/Jan/2023	Section 3.1.3: Clarified that the data will be allocated to a specific visit window based on the actual assessment date.	N/A	Provided additional clarification. No change to analysis.
Derivation of primary or secondary endpoints	31/Jan/2023	Section 3.1.3: Clarified the definition of the analysis window “Week 0 Day 1” and “Week 0 Day 1” will be only used in listings.	N/A	Provided additional clarification. No change to analysis.

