3.6 Safety outcome variables

The following safety data will be collected: reported AEs (including SAEs), haematology, clinical chemistry, urinalysis, 12-lead ECG and vital signs.

All safety measurements will use all available data for analyses, including data from unscheduled visits and repeated measurements. For lab assessment summary by visit, the data will be mapped to scheduled visits as described in Section 3.1.3.

Change from baseline to each post-baseline time point where scheduled assessments were made will be calculated for relevant measurements. AEs will be summarised by means of descriptive statistics and qualitative summaries.

No safety data will be imputed. The handling rule of partial/missing dates for AEs, prior/concomitant medications and respiratory disease history is detailed in Appendix 8.2.

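### The only between-arm ECG table uses each patient's last post-baseline reading, so it under-counts abnormality whenever the worst reading is not the last

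*SAP*

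**What the plan says.** SAP section 4.2.10.4 plans two ECG outputs. The first is a listing, in which the Investigator's assessment "will be listed for all patients, detailing whether any abnormalities were clinically significant or not". The second is a shift table: "A shift table will be produced to display normal, abnormal – not clinically significant, abnormal – clinically significant and not done". Borderline readings are counted as normal in it. The post-baseline column is then defined: "The shift table will present baseline and last observation post-baseline".

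There is no by-visit ECG table. The current text plans none, and the amendment-history rationale for section 3.1.3 agrees: "No by-visit summary for local ECG".

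The other safety shift tables follow a different rule:

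- Laboratory (section 4.2.10.2): "The shift tables will present baseline and maximum/minimum post-baseline value, as applicable for each parameter". Section 3.6.2 takes these extremes over the whole post-baseline period, post-treatment included.
- Urinalysis and white-cell CTCAE grade (sections 3.6.2 and 4.2.10.2): the maximum post-baseline value or grade.
- Vital signs (section 4.2.10.3): "Baseline to maximum post-baseline and baseline to minimum post-baseline value shift tables will be generated".

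Section 3.6 sets the general rule for which data count: "All safety measurements will use all available data for analyses, including data from unscheduled visits and repeated measurements".

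**The concern.** ECG is one of the safety endpoints named in section 1.1.3. Only an overall evaluation is recorded for it (section 3.6.4), so the SAP plans no numeric ECG summary that could show a temporary change. For laboratory values and vital signs, both the by-visit summaries and the extreme-value shift tables would reflect such a change. For ECG, the shift table is the only place where the two arms are set side by side.

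Taking the last reading makes that table depend on the order of the findings. A repeat ECG may be done because the previous one looked abnormal. If the repeat is normal, it replaces the abnormal reading in the table, so collecting more data can remove a finding from the tabulated comparison. Section 3.1.3 carries safety data through to the follow-up visit, so an ECG taken after treatment, if there is one, could displace an abnormal one recorded during treatment.

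What is at stake is how completely one safety table describes the data. Efficacy, type 1 error and power are not touched.

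**Working it through.** The SAP gives no ECG figure to reproduce, so the check compares the two rules on the same readings.

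**Inputs.** The categories come from section 4.2.10.4: normal including borderline (N), abnormal not clinically significant (NCS) and abnormal clinically significant (CS). Order them N < NCS < CS. The current rule takes the last post-baseline reading. The comparison rule takes the worst, as the other safety shift tables do. The number of post-baseline ECGs per patient is not in the SAP; section 1.2 refers to the protocol for the schedule. I therefore take it as an assumption running from one to two or more.

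**Illustrative patients.**

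| Baseline | Post-baseline readings in order | Cell under last reading | Cell under worst reading |
|---|---|---|---|
| N | CS | N to CS | N to CS |
| N | NCS, CS | N to CS | N to CS |
| N | CS, N | N to N | N to CS |
| N | CS, NCS | N to NCS | N to CS |
| NCS | CS, N | NCS to N | NCS to CS |

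**Reading the table.**

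1. With one post-baseline ECG (row 1), last and worst are the same reading and the tables agree.
2. With two or more, the tables still agree if the worst reading is the last (row 2).
3. They differ when the worst reading is earlier (rows 3 to 5). Only row 3 becomes a no-shift entry. Row 4 still shows a shift, but a milder one. Row 5 appears as an improvement.
4. The difference has one direction. The last reading belongs to the set over which the worst is taken, so it can never be the more severe of the two. In each arm, the number of patients placed in too mild a category equals the number whose worst category exceeds their last. That number is zero or more, and exactly zero if every patient has one post-baseline ECG.

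**Does another output fill the gap?** The listing holds every reading, but it gives no count by arm, and about 666 patients are to be randomised. Section 4.2.10.1 tabulates adverse events by system organ class and preferred term and summarises adjudicated MACE by arm. Those cover clinical events; they do not count ECG evaluations.

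**The case against.** The strongest defence is that this is a clear rule, fixed in advance. A reader might infer that it contradicts the all-available-data rule of section 3.6. The documents do not support that. Section 3.1.3, where it covers overall analyses and names shift tables, has all data listed and/or analysed and leaves room for exceptions specified elsewhere. Section 4.2.10.4 specifies one, and all the assessments are still listed. The charge of contradiction fails.

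A reader might also infer that transient abnormalities are lost, or that a cardiac signal is hidden. Neither follows. The readings remain in the listing with their clinical significance, an abnormality present at the last ECG is tabulated, and cardiac adverse events and adjudicated MACE are reported by arm. Nothing in the SAP shows that the under-count would favour one arm.

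The effect also depends on a schedule that is not shown. If the protocol plans one post-baseline ECG, only repeat or unscheduled ECGs could make the rules differ, and the SAP gives no rate for these. This stands, and it limits the weight of the point.

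Finally, most of the comparators are numeric with a natural maximum and minimum, whereas the ECG result is a locally read category. The last reading describes status at the end of observation, and a worst-ever rule picks up isolated readings. These are fair considerations, but urinalysis is also ordinal and is tabulated by its maximum, so a worst-category table is already within the plan's own practice.

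**Conclusion.** The point holds as a minor weakness in safety reporting. The ECG shift table departs, without a stated reason, from the extreme-value convention of every other safety shift table. It can only match or under-count post-baseline abnormality relative to that convention, and it is the only ECG table that compares the arms.

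The size is unknown. It is nil for patients with one post-baseline ECG. Otherwise it equals the number of patients whose worst category precedes a milder last one. The conclusion assumes that at least some patients have two or more post-baseline ECGs, counting repeats and unscheduled recordings.

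**What to change.** In section 4.2.10.4, define the post-baseline column as the worst category (normal or borderline < abnormal not clinically significant < abnormal clinically significant) over all scheduled, repeat and unscheduled post-baseline ECGs. This can replace the last-observation table or stand beside it. Keeping both would preserve the view of status at the end of observation.

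The cost is one line of SAP text and a small programming change. The drawback is that abnormal counts will be slightly higher, will include isolated readings, and will rise with the number of ECGs per patient. For a patient with a single post-baseline ECG, nothing changes.
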